## **RESULTS:**

Baseline patient data: Overall, 132 patients were screened for eligibility. Among them, 81 were recruited – 50 to the acupuncture arm and 31 to the SOC arm. Baseline sociodemographic and medical characteristics were similar in the two study arms as shown in Table 1. To note, all the patients randomized to the acupuncture arm were treated with acupuncture, while no patient assigned to the SOC arm received acupuncture (Fig. 1), so the planned ITT analysis was not required. In the acupuncture arm, 14 (28%) were censored (dead/discharged in the 7 days of follow-up), as compared with 8 (26%) in the SOC arm ( $p=0.87$ ). No difference in the baseline characteristics was noted between censored patients and patients completing the 7 days of follow-up.

Primary endpoint: Time-to-first delirium remission was shorter in the acupuncture arm as compared to the SOC arm ( $p<0.001$  for log-rank comparison, Fig. 2A). In the 7 days of evaluation, we calculated a number needed to treat (NNT) of 3 for first delirium remission. A multivariate Cox regression analysis was also conducted to evaluate the association of study arm allocation with the primary outcome (time-to-first delirium remission), adjusted for potential sociodemographic and medical confounders (age, gender, APACHE-II score, Charlson comorbidity index, number of psychotropic drugs, mobilization, cognitive impairment, reason for admission and type of delirium). The analysis showed that after adjusting for potential confounders, the time-to-first remission of delirium in the acupuncture arm was significantly shorter than in the SOC arm [HR 0.267 (95% CI 0.098-0.726,  $p=0.010$ ), Fig. 2B], while HR of potential confounders were not statistically significant. This means that acupuncture associated with SOC significantly increased the incidence of delirium remission by about 4-times, as compared to SOC only, after adjusting for sociodemographic and medical characteristics (model significance:  $p=0.042$ ). Furthermore, in the 7 days of evaluation, a significantly higher number of delirium-free days was found in the acupuncture arm [median 5.5 (0-6)] as compared with the SOC arm [median 0 (0-6)],  $p<0.001$ . Based on these results, the power of the study was calculated as 100%.

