1. *Delirium severity:* Comparison of the sum of long CAM-severity (CAM-S) score from day 2 (before treatment in the second day of the study) until day 7 (last day of evaluation). The CAM-S tool includes 10 delirium-related items, the first one being rated on a 0-1 scale and the nine followings in a 0-2 scale for a total score ranging from 0-19. The items include the four CAM items described earlier in addition to disorientation, memory impairment, perceptual disturbances, psychomotor agitation, psychomotor retardation and altered sleep-wake cycle. The sum of long CAM-S score has been shown to best reflect both 30-day and 90-day post-hospital outcomes in patients with delirium.
2. *Number of days an antipsychotic drug was administered:* as mentioned in the daily study investigator chart review.
3. *Pain:* based on twice daily Visual Analogue Scale (VAS) scores for communicating patients and FRAAC (Facial expression, Respiration, Activity, Audibility, Cry and consolability) scores for non-communicating patients. Both scales are rated on a 0-10 score and are comparable in terms of pain severity. They were routinely recorded twice daily by registered nurses.
4. *Sleep quality:* as assessed by the tenth CAM-S item.
5. *Delirium complications:* daily evaluation of falls, pulling-out intravenous or urinary catheters, new or increase in pressure ulcers grade.
6. *Length of hospital stay*
7. *Functional status at discharge:* based on Katz ADL at discharge as evaluated by study investigators.
8. *Safety and adverse events:* A checklist with acupuncture adverse events based on the AcupAE questionnaire was adapted to our study. All adverse events were recorded and monitored daily. Acupuncture-associated adverse events were discussed by the research team and the family of patients and addressed accordingly. Severe adverse events requiring patient exclusion

from the clinical trial included pneumothorax, massive bleeding, or infection in the acupoint area requiring systemic antibiotic treatment.

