**Statistical methods:** Demographic and clinical data was analyzed at baseline to measure the balance among the study groups. Quantitative variables were described using mean and standard deviation or median with range (minimum and maximum) depending on their distribution. Qualitative variables were described using frequency and percentage distributions. Next, we showed that our variables distribute equally between the two groups. For comparing normally distributed variables between our study groups, we used the t-test for independent samples. For comparing variables that do not distribute normally between our study groups, we used the Mann-Whitney test. For comparing qualitative variables between our study groups, we used the independent Chi-square test and Fisher exact test. Time-to-first delirium remission was evaluated using the Kaplan-Meier product limit survival estimator with log-rank between-group comparison and Cox regression was performed for multivariate adjustment of potential confounders. Hazard ratio (HR) with confidence intervals (CI) was calculated for each independent variable and controlled for all other independent variables in the regression. Patients who died or were discharged before day 7 had all subsequent days counted as the last day of evaluation in terms of both CAM and CAM-S. Intention-to-treat (ITT) analysis was planned to provide more information on the effect of the intervention. We explored the variables for possible collinearities, interaction, and confounders. All comparisons were two-sided with

significance level set at  $p<0.05$ . Data analysis was performed using IBM SPSS version 22 statistics software.

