## Secondary endpoints:

*Delirium severity:* The long CAM-S sum from day 2 to day 7 of evaluation was significantly lower in the acupuncture group [11 (24%) with no delirium, 6 (13%) with low severity, 9 (20%) with moderate severity and 19 (42%) with high severity] as compared with the control group

[3 (11%) with no delirium, 0 with low severity, 1 (4%) with moderate severity and 24 (86%) with high severity], p=0.002, Fig. 3.

*Number of psychotropic drugs-free days:* The number of psychotropic drugs-free days in the 7 days of evaluation was similar in the two study groups [median: 7 (0-7) in acupuncture arm vs 7 (0-7) in SOC arm, p=0.253].

*Pain:* No difference in daily evaluation of pain intensity was found between the two study arms in the 7 days of evaluation.

*Sleep:* According to the tenth CAM-S item daily evaluation, no difference was found in terms of quality of sleep between the study arms during the 7 days of evaluation.

*Delirium complications:* No difference was found in terms of delirium-related complications between the study arms [median: 0 (0-6) complications in acupuncture arm vs 0 (0-1) complications in SOC arm, p=0.665].

*Length of hospitalization:* The duration of hospitalization was similar in the 2 study arms [median: 13 (2-67) days in the acupuncture arm vs 12 (2-54) in the SOC arm, p=0.945].

*Functional status at discharge:* Katz ADL at discharge was similar in the two study arms [median: 2 (0-6) in the acupuncture arm vs 3.5 (0-6) in the SOC arm, p=0.945].

*Safety:* No safety event was reported according to daily AcupAE evaluation.

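### The ITT analysis is dismissed because nobody crossed over, yet the delirium-severity result covers 73 of the 81 allocated patients and omits the numeric CAM-S sum that defines the outcome

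*Combined protocol and SAP*

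**What the plan says.** All places are in the combined protocol and SAP.

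- **Statistical methods** announces an ITT analysis without defining its population: "Intention-to-treat (ITT) analysis was planned to provide more information on the effect of the intervention". It sets a carry-forward rule covering both CAM and CAM-S: "Patients who died or were discharged before day 7 had all subsequent days counted as the last day of evaluation". For non-normal quantitative variables it says: "For comparing variables that do not distribute normally between our study groups, we used the Mann-Whitney test". Qualitative variables get chi-square and Fisher tests.
- **Secondary outcomes, item 1** defines severity as a numeric quantity, "Comparison of the sum of long CAM-severity (CAM-S) score", taken from day 2 to day 7. It limits the outcome to no subset of patients.
- **Results, Baseline patient data** gives 81 recruited, 50 to acupuncture and 31 to SOC. It observes that treatment received matched allocation, "so the planned ITT analysis was not required". On early leaving it says: "In the acupuncture arm, 14 (28%) were censored (dead/discharged in the 7 days of follow-up), as compared with 8 (26%) in the SOC arm".
- **Secondary endpoints, Delirium severity** reports the acupuncture arm as "11 (24%) with no delirium, 6 (13%) with low severity, 9 (20%) with moderate severity and 19 (42%) with high severity" and the control arm as "3 (11%) with no delirium, 0 with low severity, 1 (4%) with moderate severity and 24 (86%) with high severity", with p=0.002 and a reference to Figure 3. It states no N, class cut-offs, between-arm difference or confidence interval.

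**The concern.** ITT has two parts: patients are compared in the arm to which they were allocated, and all allocated patients are in the comparison. The absence of crossover settles the first part and says nothing about the second. For severity the second part is not met.

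This matters in two ways. First, a reader told that ITT was not needed may take the severity comparison to cover all 81 patients. In an open-label trial the reasons for absence are needed to judge whether absence is related to severity or to arm. Second, the effect on the outcome as defined, the numeric sum, cannot be read from the text. Four classes without cut-offs do not give its size.

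**Working it through.** **1. Who is in the severity result.**
- Acupuncture: 11 + 6 + 9 + 19 = 45 of 50, so 5 absent (5/50 = 10.0%).
- SOC: 3 + 0 + 1 + 24 = 28 of 31, so 3 absent (3/31 = 9.7%).
- Total: 45 + 28 = 73 of 81, so 8 absent (8/81 = 9.9%).

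**2. Are 45 and 28 the real denominators?** I recomputed the rounded percentages for every N from 36 to 50 and from 23 to 31.

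| Arm | Printed | Neighbouring N | N that fits |
|---|---|---|---|
| Acupuncture | 24/13/20/42 | 44: 25/14/20/43; 46: 24/13/20/41 | 45 only |
| SOC | 11/0/4/86 | 27: 11/0/4/89; 29: 10/0/3/83 | 28 only |

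On the full arms the percentages would be 22/12/18/38 (N=50) and 10/0/3/77 (N=31). The shortfall is therefore not a misprint in one count.

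**3. Does the set match any group in the text?**
- All allocated: 50 and 31. No.
- Followed for 7 days: 50 - 14 = 36 and 31 - 8 = 23. No.
- Excluding subsyndromal patients (Table 1): 50 - 3 = 47 and 31 - 4 = 27. No.

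Since 45 exceeds 36 and 28 exceeds 23, at least 45 - 36 = 9 of the 14 and 28 - 23 = 5 of the 8 early leavers are in the result. Early leaving alone did not remove a patient.

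**4. Reproducing the printed p=0.002.** On the 2 x 4 table of the 73 patients:
- Pearson chi-square 14.37 on 3 df, p=0.0024; the exact test for the same table gives p=0.0018. Both round to 0.002.
- Mann-Whitney on the ordered classes: p=0.0009.
- Fisher, high severity against the rest: p=0.0002.

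The printed value matches a test on the classes. A rank test on the raw sums cannot be excluded, because the raw sums are not shown.

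**5. What the 8 could change.** Assumption: each absent patient could fall in any of the four classes. There are 56 ways to place 5 patients and 20 ways to place 3, so 56 x 20 = 1,120 tables of all 81. These are bounds, not probabilities.

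| Test | Range of p over 1,120 placements |
|---|---|
| Chi-square, four classes | 0.0002 to 0.073; above 0.05 in 5 |
| Mann-Whitney, ordered classes, continuity-corrected | 0.00006 to 0.036 |
| Fisher, high against rest | at most 0.011 |

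The 5 placements above 0.05 give 0.0735, 0.0695, 0.0648, 0.0543 and 0.0504. All put at least 4 of the 5 absent acupuncture patients, and none of the 3 absent SOC patients, in high severity.

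Difference in the proportion with high severity (acupuncture minus SOC, Newcombe 95% CI):

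| Scenario | Proportions | Difference, points (95% CI) |
|---|---|---|
| The 73 reported | 19/45 = 42.2%, 24/28 = 85.7% | -43.5 (-59.3 to -21.0) |
| All 81, least favourable to acupuncture | 24/50 = 48.0%, 24/31 = 77.4% | -29.4 (-46.7 to -7.5) |
| All 81, most favourable | 19/50 = 38.0%, 27/31 = 87.1% | -49.1 (-63.5 to -28.0) |
| All 8 in high severity | 24/50 = 48.0%, 27/31 = 87.1% | -39.1 (-54.4 to -18.2) |

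With all 8 in high severity, chi-square p=0.0038 and Mann-Whitney p=0.0011. The document prints no difference or interval. Those in this table are my calculations on a split that it does not itself test.

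**The case against.** **The figures may explain the 8.** The ITT sentence cites Figure 1, a CONSORT flow diagram, and the severity result cites Figure 3. Neither is shown. This stands: I can say that the readable text gives no reason, not that the trial gives none. It does not rescue the inference, since a flow diagram would not make absence of crossover equivalent to complete inclusion.

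**The sentence is right in its own terms.** It says that treatment received and treatment allocated coincide, and they do. Statistical methods sets no rule that every patient must be in every secondary outcome, and no similar gap is readable for the primary outcome. This also stands, and it confines the point to the severity result.

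**There is a plausible innocent reason.** The sum starts on day 2, assessment stops at discharge, and the shortest stay is 2 days in both arms, so some patients may have no assessment from day 2 onward. The carry-forward rule does not clearly extend to patients assessed only on day 1. This is possible, but the text does not give it as the reason.

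**The denominators are recoverable and the result is robust.** Both are true. The counts are printed and lead directly to 45 and 28.

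A reader might infer that the severity finding is wrong, or that patients were removed selectively. The documents support neither: absence is almost equal between arms, and no placement of the 8 reverses the direction. Nor can the effect be called less certain than printed, because no effect size is printed.

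**Conclusion.** The point holds for one secondary outcome. No crossover does not make an ITT analysis unnecessary, and here 8 of the 81 allocated patients have no reported severity value. The outcome as defined is not readable as a numeric result.

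The conclusion on direction is not in doubt. The size is open: with all 81 included, the high-severity difference could be anywhere from -29.4 to -49.1 points, against -43.5 in the 73. This rests on the counts being correct, which the percentages confirm, and on the assumption that an absent patient could fall in any class. Whether the absences are explained in Figures 1 or 3 cannot be judged from the text. Priority is minor to moderate.

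**What to change.** 1. Replace the statement that ITT was not required with: patients were analysed as allocated; severity is available for 45/50 and 28/31. Give the reasons for the 5 and the 3.
2. Report the numeric long CAM-S sum over days 2 to 7 by arm, in all patients whose sum can be recovered from the daily records, with a difference and 95% CI. Use the t-test or Mann-Whitney comparison and the carry-forward rule in Statistical methods, and state how a patient assessed only on day 1 is treated.
3. Beside it, show a model adjusted for the baseline long CAM-S already collected, labelled post hoc. Allocation followed the weekday of diagnosis (Randomization), so balance in baseline severity does not rest on chance. Table 1 shows similar medians (8 and 9, p=0.63), so the adjustment is a check and a likely gain in precision, not the repair of a known imbalance.
4. If some sums cannot be recovered, call the result an available-patient analysis and give the bounds above for all 81 as a sensitivity analysis.
5. Keep the four classes as description, state their cut-offs, and name the test behind p=0.002.

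Cost: one small re-analysis of existing records and a few sentences, with no new patients. The adjusted result will be post hoc, and the p-value may become less extreme.

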**Sample size calculation:** Since no previous study has evaluated an acupuncture-based intervention in older adults with delirium, a pilot study of 32 patients [acupuncture group (n=24); control group (n=8)] was designed to estimate accurately the sample size for our current study. In the pilot study, delirium-free days were  $3.2 \pm 1.6$  in the acupuncture group as compared with  $1.7 \pm 2.4$  in the control group. Taking into account a Type I error (alpha) of 0.05, a power of 0.80, pairwise comparison between our two study arms, and using G\*Power 3.1.9.4 software, we calculated a minimal sample size of 28 patients in each of the 2 study arms.

**Randomization:** Patients were randomized in two groups by convenience allocation according to acupuncturists' working days: patients with delirium diagnosed on Sunday, Monday, Wednesday or Thursday were assigned to the acupuncture arm, while patients with delirium diagnosed on Tuesday, Friday or Saturday were assigned to SOC arm. Blinding was clearly not feasible.

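### Collected baseline CAM-S and ADL are left out of the analyses they would sharpen, the planned CAM-S sum is reported as four bands in 73 of 81 patients, and the adjusted remission effect is summed up without its wide interval

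*Combined protocol and SAP*

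**What the plan says.** **Severity.** Secondary outcomes (Delirium severity) defines the endpoint as a comparison of the summed long CAM-S from day 2 to day 7. Statistical methods adds that patients who died or left before day 7 "had all subsequent days counted as the last day of evaluation in terms of both CAM and CAM-S". Results gives the counts with no, low, moderate and high severity: 11, 6, 9 and 19 on acupuncture against 3, 0, 1 and 24 on SOC, p=0.002.

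**Function.** Results reports a median discharge Katz ADL of 2 (acupuncture) against 3.5 (SOC), p=0.945, and calls the arms similar. The p for length of stay is also 0.945.

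**Baselines.** Table 1 has long CAM-S of 8 vs 9 (p=0.63) and ADL of 4.5 vs 4 (p=0.36).

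**Primary endpoint.** Statistical methods states that "Cox regression was performed for multivariate adjustment of potential confounders" and that "Hazard ratio (HR) with confidence intervals (CI) was calculated for each independent variable". It does not name the covariates, their coding or the handling of ties. Results lists nine covariates besides arm: "age, gender, APACHE-II score, Charlson comorbidity index, number of psychotropic drugs, mobilization, cognitive impairment, reason for admission and type of delirium". It prints HR 0.267 (95% CI 0.098-0.726, p=0.010) and concludes that acupuncture with SOC "significantly increased the incidence of delirium remission by about 4-times".

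**The concern.** A score measured before treatment usually predicts the same score afterwards, so leaving it out gives up precision at no saving. For severity, banding also discards information from the score that was planned as the endpoint, and ignoring the order of the bands discards more. Eight patients have no band, although the carry-forward rule should give a value to anyone who left early.

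For ADL, the acupuncture median starts 0.5 higher and ends 1.5 lower. A test of discharge values alone cannot take the starting level into account, and a p-value shared with a different endpoint may be a copying error.

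For remission, Randomization says "Patients were randomized in two groups by convenience allocation", by weekday of diagnosis. Readers will therefore look to the adjusted estimate for the size of the effect, and the text sums it up in one rounded figure.

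**Working it through.** **1. Severity bands.** Acupuncture 11+6+9+19 = 45 of 50; SOC 3+0+1+24 = 28 of 31. Total 73 of 81, so 5 and 3 are absent.
- Unordered Pearson chi-square, 3 df: 14.37, p=0.0024. This reproduces the printed 0.002.
- Mann-Whitney on the ordered bands: p=0.0009.
- Worst case, with the 5 acupuncture patients placed in high severity and the 3 SOC patients in no delirium: 11/6/9/24 vs 6/0/1/24. Chi-square p=0.019, Mann-Whitney p=0.036. The direction holds.

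**2. Possible gain from baseline.** The variance of an adjusted difference is proportional to 1 - r². The documents give no baseline-outcome correlation r. With r assumed at 0.3, 0.5 or 0.7, the variance falls by 9%, 25% or 49%.

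**3. ADL.** Acupuncture 2 - 4.5 = -2.5; SOC 3.5 - 4 = -0.5. These are differences of medians, not median changes.

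**4. The printed hazard ratio.** SE of log HR = (ln 0.726 - ln 0.098)/3.92 = 0.511. z = ln(0.267)/0.511 = -2.58, two-sided p=0.0097, which matches 0.010. Inverted: 1/0.267 = 3.75, with limits 1/0.726 = 1.38 and 1/0.098 = 10.2.

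**5. Parameters.**
- One term per variable: arm + 9 = 10.
- Reason for admission (6 levels) and delirium type (4 levels) as categories: 1 + 5 single terms + mobilization 1 + cognition 1 + 5 + 3 = 16.
- Mobilization and cognition (4 levels each) as categories too: 1 + 5 + 3 + 3 + 5 + 3 = 20.

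**6. Remissions.** The text gives no count, but two statements bound it. Delirium-free days were "found in the acupuncture arm [median 5.5 (0-6)] as compared with the SOC arm [median 0 (0-6". A median of 5.5 in 50 patients needs at least 26 remissions; a median of 0 in 31 allows at most 15. The second statement is "a number needed to treat (NNT) of 3 for first delirium remission". If the NNT is rounded to the nearest whole number, the risk difference lies between 1/3.5 and 1/2.5.
- The total is then 30 (26+4) to 59 (44+15), with 4-15 on SOC. If the NNT was rounded up, it is 27-64, with 1-15 on SOC.
- Remissions per parameter run from 30/20 = 1.5 to 59/10 = 5.9.

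This assumes whole-day scores for all 81 patients, at least one delirium-free day after any remission, and an NNT from crude proportions.

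**7. Source of the width.** With no covariates, an approximate SE from 26 and 4 remissions is √(1/26 + 1/4) = 0.54, already as large as 0.511. With 44 and 15 it is √(1/44 + 1/15) = 0.30, which would leave room for a covariate effect. A simulation used the Table 1 category counts, 27% early exit and covariates with no effect. Against a five-term model, the SE was 2-5% larger with 10 parameters, 6-12% with 16 and 12-20% with 20. Dividing 0.511 by 1.02 gives an interval of about 1.40-10.0; dividing by 1.20 gives about 1.63-8.6. It is wide either way.

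**8. Direction of bias.** In the same simulation, the error of the median estimate against a true ratio of 3.75 was:

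| Parameters | Breslow ties | Efron ties |
|---|---|---|
| 10 | -14% to +5% | +7% to +15% |
| 16 | -11% to +16% | +15% to +33% |
| 20 | -8% to +27% | +23% to +47% |

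Neither coding nor tie method is stated, so the sign is open.

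**The case against.** The interval is not hidden: Results prints it in the sentence before the four-fold statement, Figure 2 repeats it, and 3.75 is about 4. This stands, and reduces the primary-endpoint point to one of presentation.

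A reader might infer that too many covariates caused the imprecision, or inflated the effect. The documents support neither. Steps 7 and 8 show that a small SOC event count could produce the width alone and that the sign of any bias depends on unstated details. On the literal reading of one hazard ratio per variable, the model has 10 parameters and the simulated error is modest.

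A short model is not clearly better. Under weekday allocation it may drop real confounders: normal mobility is 24 of 50 against 9 of 31, and normal cognition 28 of 50 against 12 of 31. In a check with about 34 remissions and Efron ties, impaired mobility and impaired cognition were each given an assumed remission HR of 0.61 or 0.45. A five-term model omitting both was off by +30% or +24%; the 10-parameter model was off by +38% or +25%. This is why the short model belongs in a sensitivity analysis only.

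A reader might also take the absence of baseline CAM-S for confounding. The medians are 8 and 9 (p=0.63), so it is a missed gain in precision. Nor do the ADL medians show harm: Table 1 does not name the ADL instrument or its timing, and differences of medians are not patient-level changes.

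Unadjusted two-group tests are the stated plan, and this is fair for ADL. For severity, though, the stated plan for a quantitative score is a t-test or Mann-Whitney test, not a chi-square on bands. Finally, Figures 1 to 3 could not be read in the copy reviewed, so they may give the remission counts or account for the 8 patients.

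**Conclusion.** The point holds as one about unused baseline data and the reporting of effect size. It should be acted on but changes no main conclusion.

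- **Severity:** the analysis departs from the defined endpoint, ignores order and leaves out 8 of 81 patients. Carry-forward means early exit alone does not explain them. The difference survives the worst-case placement.
- **ADL:** the claim of similarity rests on a test that does not use baseline and on a p-value that needs checking.
- **Remission:** the adjusted effect is 3.75 (1.38-10.2), assuming the printed HR compares SOC with acupuncture, as the text's own reading requires. The shares of the width due to few SOC remissions and to 10-20 parameters cannot be separated without the counts per arm.

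A reader might go on to doubt that remission differed at all. Nothing here supports that: the log-rank and delirium-free-day comparisons (both p<0.001) do not use the Cox model, and the adjusted interval excludes a ratio of 1.

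**What to change.** 1. Analyse the day 2-7 CAM-S sum as a continuous or ordinal score with baseline long CAM-S as covariate. Include the 8 patients or explain their absence, and show the worst-case check.
2. Analyse discharge Katz ADL with baseline ADL as covariate, after confirming that the baseline measure is the same instrument. Re-check p=0.945 for both ADL and length of stay.
3. Replace the four-fold statement with 3.75 (95% CI 1.38-10.2), beside the unadjusted HR and remissions per arm. State the factor coding and tie method.
4. Keep the reported nine-covariate model. Add, labelled as a post hoc sensitivity analysis, a shorter model that includes arm and baseline CAM-S, with covariates chosen on clinical grounds and a tie method suited to daily assessment (Efron, exact or discrete-time).

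Cost: changes to wording and a re-run on variables already collected. The shorter model is chosen after the results are known and may omit confounders, and estimates may move in either direction.

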**Treatment regimen:** The number of acupuncture treatments was set at up to five treatments in the one-week study period (treatments was not provided on weekends) or until the patient is delirium-free for 48 hours. Each session lasted 15-20 minutes.

**Other components of treatment:** Patients of acupuncture group also received SOC. Prior to the start of the study, a multicomponent protocol for delirium management was developed and implemented in internal medicine departments. This protocol was based on best literature evidence, current practice guidelines and the opinions of geriatric and psychiatric consultants, and included both pharmacological and non-pharmacologic interventions as published in a preceding manuscript. All clinicians working in the internal medicine departments were educated regarding the protocol and its use. This protocol was defined “SOC” for the study. Since the actual care of patients may differ according to clinical data and physician consideration, the use of psychotropic drugs (including antipsychotics) during hospitalization were documented and compared between the study arms. No other complementary medicine therapies other than acupuncture were added. Explanations were given to patients and their next-of-kin on potential benefits and side effects of acupuncture and treatment was administered only after they signed informed consent.

**Practitioner background:** The treatment was administered by seven acupuncturists with at least 5 years of clinical experience in a hospital setting.

**Control intervention:** In the control group, patients received SOC only.

**Outcomes:** All daily outcomes were collected daily for one week after randomization or until the patient was discharged from the hospital.

Primary outcome: Our primary endpoint was resolution of delirium during the 7 days of evaluation and was measured as time-to-first remission of delirium and number of delirium-free days, based on daily assessment of CAM scale.

Secondary outcomes:

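### Delirium-free days, the primary measure used to size the trial, is compared only without adjustment although arms were formed by weekday; the net bias in that comparison is unknown

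*Combined protocol and SAP*

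**What the plan says.** All references are to the combined protocol and SAP.

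- **Methods, Outcomes.** Resolution of delirium over 7 days "was measured as time-to-first remission of delirium and number of delirium-free days". Neither measure is ranked above the other.
- **Methods, Sample size calculation.** The calculation uses pilot delirium-free days only (3.2 ± 1.6 vs 1.7 ± 2.4) and concludes: "we calculated a minimal sample size of 28 patients in each of the 2 study arms".
- **Methods, Randomization.** "Patients were randomized in two groups by convenience allocation according to acupuncturists' working days". Four weekdays led to acupuncture and three to standard of care, without blinding.
- **Methods, Statistical methods.** Quantitative variables get a t-test or, if not normal, a Mann-Whitney test. The only multivariable method appears with time to first remission: "Cox regression was performed for multivariate adjustment of potential confounders".
- **Results, Primary endpoint.** The Cox model for time to first remission has nine covariates (HR 0.267, 95% CI 0.098-0.726, p=0.010). For the other measure the text says that "a significantly higher number of delirium-free days was found in the acupuncture arm", with medians 5.5 (0-6) vs 0 (0-6), p<0.001. The test is not named there; Mann-Whitney is inferred from the Methods rule and the use of medians. Either listed two-sample test would be unadjusted.
- **Results, Baseline patient data.** The arms are described as similar on the strength of Table 1.

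**The concern.** Random allocation is what normally justifies an unadjusted comparison. Here the arms follow the calendar, and the plan itself treats confounding as worth adjusting for on one primary measure. It gives no reason for leaving out the other, which is the one the trial was designed around.

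The unadjusted p-value for delirium-free days therefore carries whatever baseline differences exist between the arms. A reader cannot tell how much of the difference in days would remain among comparable patients. The Cox result does not fill the gap: a hazard ratio for first remission does not translate into days free of delirium, the quantity in which the planning effect (1.5 days) was stated.

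**Working it through.** **1. The plan's own figure.** Inputs from the sample size paragraph: difference 3.2 − 1.7 = 1.5 days, alpha 0.05, power 0.80, two-sided. With the mean of the two pilot SDs, (1.6 + 2.4)/2 = 2.0:

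n per arm = 2(1.960 + 0.842)² × 2.0² / 1.5² = 27.9, so 28.

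This matches the stated 28 and confirms that delirium-free days is the sizing measure. (The root-mean-square SD, √[(1.6² + 2.4²)/2] = 2.04, gives 30.)

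**2. Baseline gaps from the Table 1 counts.** Standardized difference = (p₁ − p₂) / √{[p₁(1−p₁) + p₂(1−p₂)]/2}.

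| Factor | Acupuncture | SOC | Std. difference | Plausibly favours acupuncture? |
|---|---|---|---|---|
| Normal mobilization | 24/50 (48%) | 9/31 (29%) | 0.40 | yes |
| Hearing/visual impairment | 26/50 (52%) | 22/31 (71%) | −0.40 | yes |
| Normal cognition | 28/50 (56%) | 12/31 (39%) | 0.35 | yes |
| Bedridden | 9/50 (18%) | 4/31 (13%) | 0.14 | no |
| Subsyndromal | 3/50 (6%) | 4/31 (13%) | −0.24 | arguably no |

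Table 1 prints 19% for 9/31; the count gives 29%, and the printed p=0.19 reproduces from the counts. Median APACHE-II is 9 vs 11. Prevalent delirium (52% vs 52%) and Charlson index (7 vs 7) are level. The smallest Table 1 p-value is 0.11, but non-significance with 50 vs 31 patients does not show balance.

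**3. What gaps of this size could do.** Null simulation, 1,500 data sets per setting: no acupuncture effect, 50 vs 31 patients, a 0-6 day score, cognition and mobilization fixed at the Table 1 counts. Assumptions: a 1.5-point APACHE-II gap, odds ratios of 2 to 4.5 for each of cognition and mobilization, and 1.07 to 1.16 per APACHE-II point.

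- Mann-Whitney false-positive rate at 0.05: about 10-26%.
- Spurious gain: about 0.45-0.85 day.
- Rank regression on the same three covariates: 5-6%.
- Weaker effects (odds ratio 1.5; 1.05 per APACHE-II point): 8% and 0.29 day.
- No APACHE-II gap: 8-14%.
- Frequency of p<0.001 with odds ratios 2 to 4.5 in a closely similar model: only about 0.3-1.3%.

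**4. Against the observed difference.** The documents give medians, not a mean difference. Three constructed 0-6 day data sets (assumption) with 50/31 patients, medians 5.5 and 0, and Mann-Whitney p between 3×10⁻⁶ and 1×10⁻⁴ have mean differences of about 2.3-2.8 days. Subtracting a fixed shift and applying a Welch test:

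- 0.5 day removed: p = 0.00002 to 0.0016
- 0.83 day: 0.0002 to 0.009
- 1.0 day: 0.0006 to 0.021
- 1.5 days: 0.012 to 0.15

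A bias at the top of the simulated range could cost p<0.001. In these data sets, losing p<0.05 takes more than 1 day.

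**5. Does the adjusted Cox result show confounding?** ln(0.267) = −1.321; SE = (ln 0.726 − ln 0.098)/3.92 = 0.511; z = −2.58; p = 0.0097, agreeing with the printed 0.010. The unadjusted hazard ratio is not reported. Assume 30-40 remissions vs 8-14, consistent with the stated NNT of 3 (30/50 − 8/31 = 0.34; 40/50 − 14/31 = 0.35). The unadjusted SE is then about √(1/30 + 1/8) = 0.40 to √(1/40 + 1/14) = 0.31. The *same* hazard ratio gives |z| = 1.321/0.40 = 3.30 to 1.321/0.31 = 4.26, which is p<0.001 throughout. The move from p<0.001 to 0.010 can be entirely loss of precision.

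**The case against.** The strongest defence has four parts.

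- **The companion measure was adjusted and held up.** It comes from the same daily CAM, and its model included cognition, mobilization and APACHE-II. This stands as partial reassurance, but it gives no adjusted size for the difference in days.
- **The gaps run both ways, and no covariate was significant in the Cox model.** The first part stands, and is why the net direction cannot be asserted. The second carries little weight with nine covariates in 81 patients. Equally, the documents do not support odds ratios as high as 4.5, so the simulated range is illustrative.
- **The printed result is p<0.001, not p<0.05.** This stands. A reader might infer that baseline differences explain the finding; the simulation does not support that, since p<0.001 was rare under every setting tried.
- **Adjustment cannot repair weekday allocation.** It cannot remove unmeasured or assessment bias. It can address measured differences, which the plan already attempted for the other measure.

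Two further readings are tempting. A reader might take the change from log-rank p<0.001 to Cox p=0.010 as proof of confounding; step 5 of the working shows why it is not. A reader might also take the delirium-free-days result as offered in independent support of the Cox result; the Results merely report it next, and both measures share the same assessments.

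**Conclusion.** The concern holds as a gap in the analysis. One of two primary measures, and the only one behind the sample size, has no covariate-adjusted estimate although allocation was not by chance. The net bias in the 5.5 vs 0 comparison is unknown in size and direction. Under the assumed prognostic effects it could be about 0.45-0.85 day, which is 30-57% of the 1.5-day planning effect (0.45/1.5; 0.85/1.5). Against the illustrative observed difference it is a smaller share, roughly 16-37% (0.45/2.8; 0.85/2.3). These figures rest on assumed odds ratios, an assumed APACHE-II gap and constructed outcome data; an actual adjusted estimate needs patient-level data. The documents do not show that the result would disappear. The change should be made because it is cheap and the size of effect on this measure cannot otherwise be judged.

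**What to change.** Add a covariate-adjusted analysis of delirium-free days. A suitable choice is proportional-odds regression of days (0-6) on arm with a short list: IQCODE category, mobilization, APACHE-II and baseline long CAM-S. All are in Table 1; sparse IQCODE and mobilization categories should be merged. Report the common odds ratio with 95% CI beside the unadjusted test, and name that test. Label the analysis as added after the results were seen. Base the statement about this measure on the adjusted estimate, and say plainly that adjustment cannot remove unmeasured or assessment bias from a predictable, unblinded weekday allocation.

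Cost: one regression on data already held, a proportional-odds assumption to check, and probably a less extreme p-value.
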